8.5.11 Pregnancy

There has been no experience to date of the use of tazemetostat during pregnancy or lactation. In an embryofetal development study, evidence of increased skeletal developmental abnormalities in fetuses from the pregnant rats and rabbits relative to fetuses from control rats and rabbits were observed. Consequently, there is a potential risk for teratogenicity, and precautions must be taken to avoid any pregnancy that could potentially be conceived during exposure to tazemetostat by EITHER male OR female subjects.

Sexually active male subjects must ensure that acceptable methods of contraception are used throughout the study period, including the post-treatment period as described in the sections below, if their partner is or could become pregnant.

8.5.11.1 Definition of Childbearing Potential: Female Subjects

A female subject is considered of childbearing potential if she:

- Is anatomically and physiologically capable of becoming pregnant, and
- Will be or could possibly be sexually active with a male while undergoing study treatment with the possibility of posing harm to a fetus

A female subject is considered to be of non-childbearing potential (i.e., physiologically incapable of becoming pregnant) if she:

- Is surgically sterilized (i.e., bilateral tubal ligation, total hysterectomy, or bilateral oophorectomy) with surgery at least 1 month before the first dose of study treatment
- Has a documented congenital or acquired disorder that is incompatible with pregnancy

8.5.11.2 Definition of Childbearing Potential: Male Subjects

A male subject is considered of childbearing potential if he:

- Is anatomically and physiologically capable of causing a pregnancy in a female partner, and
- Will be or could possibly be sexually active with a female (who is or may become pregnant) while undergoing study treatment with the possibility of posing harm to a fetus

A male subject is considered to be of non-childbearing potential if he:

- Has a documented successful vasectomy (with confirmed azoospermia)

8.5.11.3 Pregnancy Testing

All female subjects of childbearing potential must have a negative pregnancy test (urine or serum) at Screening and within 72 hours of the first dose of study treatment.

Subsequent pregnancy tests performed every 4 weeks after first dose of study treatment may be either urine or serum. Positive urine tests are to be confirmed by serum testing.

8.5.11.4 Prevention

8.5.11.4.1 Female Subjects

Females of childbearing potential must agree to use a highly effective method of contraception that results in a failure rate of < 1% per year when used consistently and correctly, starting at least 7 days before starting tazemetostat, during study treatment, and for 6 months after the final dose of study treatment, **and** have a male partner who uses a condom when using hormonal contraceptive.

Acceptable highly effective contraception includes:

- Placement of an intrauterine device
- Established hormonal contraceptive methods: oral, injectable, or implant.

NOTE: Female subjects who are using hormonal contraceptives must have been on a stable dose of the same hormonal contraceptive product for at least 4 weeks prior to the first dose of study treatment and must continue to use the same contraceptive during study treatment and for 6 months after discontinuation of study treatment.

Due to the potential of enzyme induction with tazemetostat, female subjects who use hormonal contraceptives should use an additional barrier method of birth control while on study treatment and for 6 months after discontinuation of study treatment.

Female subjects exempt from this requirement are subjects who practice true abstinence when this is in line with the preferred and usual lifestyle of the subject (periodic abstinence [e.g., calendar, ovulation, symptothermal, post-ovulation methods], declaration of abstinence for the duration of the trial, and withdrawal are not acceptable methods of contraception), or have a male partner who is vasectomized. If currently abstinent, the subject must agree to use a highly effective method of contraception as

described above if they become sexually active during study treatment, and for 6 months after discontinuation of study treatment.

8.5.11.4.2 Male Subjects

Male subjects of childbearing potential must agree to use condoms with their female partner of child bearing potential starting from the first dose of tazemetostat, throughout study treatment, and for 3 months after the final dose of study treatment.

8.5.11.5 Reporting of Pregnancy

Pregnancy will not be considered an SAE. Any report of pregnancy recorded for any female subject or a female partner of a male subject should be reported. To ensure subject safety, each pregnancy must be reported to the Sponsor or its designee within 2 weeks of learning of its occurrence using a clinical trial pregnancy report form. A Pregnancy Report Form should be completed and submitted by email and/or fax to the Sponsor or its designee.

The pregnant female subject must be withdrawn from the study. Every effort should be made to gather information regarding the pregnancy outcome until eight weeks post-partum. It is the responsibility of the Investigator to obtain all pregnancy information.

Pregnancy complications and elective terminations for medical reasons must be reported as an AE or SAE. Spontaneous abortions must be reported as an SAE.

Any SAE occurring in association with a pregnancy brought to the Investigator's attention after the subject has completed the study and considered by the Investigator as possibly related to the study treatment, must be promptly reported to the Sponsor.

The Investigator also must attempt to collect and report to the Sponsor or its designee pregnancy information on any female partner of male study subjects who become pregnant while the subject is enrolled in the study.

9 WITHDRAWAL AND REPLACEMENT OF SUBJECTS

9.1 Withdrawal of Subjects from Treatment/Procedures

Subjects have the right to withdraw from the study at any time and for any reason without prejudice to future medical care by the physician or institution.

Subjects (or legally authorized representatives) can decline to continue receiving tazemetostat and/or other protocol-required procedures at any time during the study but can continue participation in the study (e.g., for follow-up information). If this occurs the Investigator is to discuss with the subject appropriate processes for discontinuation and the options for procedures that may continue such as collection of data, including endpoints and AEs. The Investigator must document the agreement in the procedures that the subject will continue with and the level of follow-up that is agreed to by the subject (e.g., in person, by telephone/mail, through family/friends, in correspondence/communication with other physicians, from review of the medical records.)

Reasons for removal from protocol-required treatment or procedures might include the following:

- Disease progression
- Subject request to end study treatment and/or procedures
- Safety concern (e.g., AE, failure to follow contraception or pregnancy, excluded medication required)

9.2 Withdrawal of Subjects from Study

Withdrawal of full consent for a study means that the subjects does not wish to receive further protocol-required treatment, procedures and does not wish to or is unable to continue further study participation. Subject data up to withdrawal of consent will be included in the analysis of the study, and where permitted, publicly available data can be included after withdrawal of consent (e.g., death records). The Investigator must document this agreement regarding withdrawal of full consent as well as discuss appropriate procedures for withdrawal from the study.

Reasons for removal of a subject from the study might include the following:

- Death
- Decision by Sponsor to terminate the study
- Subject request to withdraw from study
- Lost to follow-up

9.3 Replacement of Subjects

A subject will be replaced during dose escalation if the subject:

- Is removed from a cohort during Cycle 1 for reasons other than toxicity (opinion of the Investigator will be consulted) or
- Has an interruption in dosing during Cycle 1 of more than 14 days total.

Subjects will not be replaced during the Dose Expansion portion of the trial.

9.4 Survival Follow-Up

Subjects who discontinue study treatment for reasons other than disease progression will continue to have disease assessments, when possible, every 8 weeks until disease progression or death. In addition, subjects who permanently discontinue study treatment will be followed (by phone, email, or clinic visit) for survival every 16 weeks until death, withdrawal of consent, or they are lost to follow-up. AESI and subsequent anti-cancer therapy information will be collected throughout the survival follow up.

Survival follow-up will continue for 2 years for each subject or until 80% of subjects enrolled have died.

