Dose Expansion: Approximately 72 subjects will be enrolled into the dose expansion into the following cohorts:

- Cohort 1 – approximately 20 subjects with ATRT
- Cohort 2 – approximately 20 subjects with MRT/RTK/selected tumors with rhabdoid features
- Cohort 3 – approximately 20 subjects with INI1-negative tumors as follows:
 - Epithelioid sarcoma
 - Epithelioid malignant peripheral nerve sheath tumor
 - Extraskeletal myxoid chondrosarcoma
 - Myoepithelial carcinoma
 - Renal medullary carcinoma
 - Chordoma (poorly differentiated or de-differentiated)
 - Other INI1-negative malignant tumors with Sponsor approval
- Cohort 4 – up to 12 subjects with one of the tumor types defined in Cohorts 1 through 3 or synovial sarcoma with SS18-SSX rearrangement (Closed to enrollment after sufficient PK data were collected).

**Diagnosis and Main
Criteria for Inclusion:**

Inclusion Criteria

For All Subjects: Subjects must meet ALL of the following criteria to be eligible for enrollment in this study.

1. Age (at the time of consent/assent): ≥ 6 months to < 18 years of age
 - Cohort 4 only: ≥ 10 years to < 18 years
2. Performance Status:
 - If < 12 years of age: Lansky Performance Status $> 50\%$ (see [Appendix 1](#))
 - If ≥ 12 years of age: Karnofsky Performance Status $> 50\%$ (see [Appendix 2](#))

NOTE: If subject is unable to walk due to paralysis, but is mobile in a wheelchair, subject is considered to be ambulatory for the purpose of assessing their performance status.
3. Has provided signed written informed consent/assent
4. Has a life expectancy of > 3 months

5. Has relapsed or refractory disease and no standard treatment options as determined by locally or regionally available standards of care and treating physician's discretion
6. Is ineligible or inappropriate for other treatment regimens known to have effective potential
7. Has a documented local diagnostic pathology of original biopsy confirmed by a Clinical Laboratory Improvement Amendments (CLIA)/College of American Pathologists (CAP) or other Sponsor-approved laboratory certification
8. Has all prior treatment (i.e., chemotherapy, immunotherapy, radiotherapy) related clinically significant toxicities resolve to \leq Grade 1 per CTCAE, version 4.03 or are clinically stable and not clinically significant, at time of enrollment
9. Prior therapy(ies), if applicable, must be completed according to the criteria below:

Prior Therapy	Time from Last Prior Therapy

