2 OBJECTIVES AND ENDPOINTS

Objectives	Endpoints
Primary: Dose Escalation	

 To determine the MTD or the RP2D of tazemetostat when administered as an oral suspension BID in pediatric subjects with relapsed/refractory rhabdoid tumors, INI1-negative tumors, or synovial sarcoma 	
 Incidence and severity of TEAEs qualifying as protocol-defined DLTs in Cycle 1 Establishment of the protocol-defined RP2D and/or MTD
Primary: Dose Expansion	

 To evaluate the antitumor activity of tazemetostat as assessed by overall response rate (ORR) in in pediatric subjects with relapsed/refractory atypical teratoid rhabdoid tumor (ATRT) (Cohort 1), non-ATRT rhabdoid tumors (Cohort 2), INI1-negative tumors (Cohort 3), and tumor types eligible for Cohorts 1 through 3 or synovial sarcoma with SS18-SSX rearrangement (Cohort 4) using disease-appropriate standardized response criteria 	
 ORR: CR + PR for each cohort
Secondary: Dose Escalation	

 To evaluate the preliminary antitumor activity of tazemetostat as assessed by ORR, using disease-appropriate standardized response criteria 	
 ORR: CR + PR
Secondary: Dose Expansion	

 To determine the PFS and overall survival (OS) at 24 and 56 weeks and overall pediatric subjects with relapsed/refractory ATRT (Cohort 1), non-ATRT rhabdoid tumors (Cohort 2), INI1-negative tumors (Cohort 3), and tumor types eligible for Cohorts 1 through 3 or synovial sarcoma with SS18-SSX rearrangement (Cohort 4) using disease-appropriate standardized response criteria 	
 PFS at 24 and 56 weeks and overall for each cohort OS at 24 and 56 weeks and overall for each cohort
Secondary: All Subjects	

 To assess the safety and tolerability of tazemetostat administered as an oral suspension BID and tablet three times daily (TID) 	
 AEs, clinical laboratory tests, and other safety measures

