3.5.2 End of Study

Primary completion: This includes time until the last subject is assessed or receives an intervention for the purposes of final collection of data for the primary analysis of the study. The primary completion is expected to occur approximately 6 months after the date the last subject is enrolled to treatment and evaluated for response.

End of study: This includes time when the last subject is assessed or receives an intervention for evaluation in the study. The end of study will occur when the last subject discontinues the study treatment and has had the opportunity to complete the safety follow-up visit or the long-term survival follow-up period, whichever is later. The study may end prior to this if 80% of enrolled subjects are deceased prior to the collection of the last survival follow-up.

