4 SUBJECT POPULATION

4.1 Number of Subjects

A total of approximately 120 subjects will be enrolled in this study. Up to 48 subjects are estimated to be enrolled during dose escalation (subjects who discontinue in absence of a DLT prior to the completing of the DLT evaluation period may be replaced). Up to 72 subjects are estimated to be enrolled during Dose Expansion. See Section 14.2.1 for sample size assumptions.

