14.2 Study Design Considerations

14.2.1 Determination of Sample Size

Dose Escalation: The sample size is not based on a statistical consideration. The number of subjects will be determined based in part on the number of dose escalations required to determine the protocol-defined MTD and/or RP2D. It is expected that approximately 48 subjects will be enrolled with the "Rolling 6" dose-escalation design (subjects who discontinue in absence of a DLT prior to the completing of the DLT evaluation period may be replaced).

Dose Expansion: The sample size for dose expansion (Cohorts 1 to 3) is based on the hypothesized improvement in ORR over historical rates. An ORR no higher than 5% would have no clinical benefit over existing therapies; an ORR of 20% is considered of clinical interest. For each Dose Expansion cohort separately, using a one-sided test and targeting a Type I error rate of 10% and a Type II error rate of 20% requires a total of 20 pediatric subjects to be enrolled per cohort in Cohorts 1 to 3. To establish that the data support tazemetostat, at least 3 of 20 subjects will be required to have an objective response (i.e., an observed 15% ORR) within a cohort. Due to the discrete nature of the primary endpoint, this statistical test achieves a Type I error rate of 8% (i.e., probability of deciding for tazemetostat when the true ORR is 5%), and a Type II error rate of 21% (i.e., probability of deciding against tazemetostat when the true ORR is 20%).

Twelve subjects were to be enrolled in dose expansion Cohort 4 to evaluate the PK of tazemetostat when administered as a tablet formulation to pediatric subjects. Sufficient information to describe the PK of tazemetostat was obtained after administration of tazemetostat tablets to 4 pediatric subjects. Therefore, Cohort 4 was closed to further enrollment. Approximately 72 subjects will be enrolled across the 4 Dose Expansion cohorts.

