The completion of the primary endpoint of the study is expected to occur approximately 6 months after the date the last subject is enrolled to treatment and evaluated for response. The end of study will occur when the last subject discontinues the study treatment and has had the opportunity to complete the safety follow-up visit (30 days after last dose of tazemetostat) or the long-term survival follow-up period (2 years from first dose of tazemetostat), whichever is later. The study may end prior to this if 80% of enrolled subjects are deceased prior to the collection of the last survival follow-up.

Survival follow-up will continue for 2 years for each subject or until 80% of treated subjects have died.

All patients are to discontinue participation on the study after 2 years of cumulative treatment, regardless of whether they came off study due to clinical response or if they reduced dose.

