4.3. FINAL ANALYSIS OF PROGRESSION-FREE SURVIVAL AND OVERALL SURVIVAL

Depending on the maturity of PFS and OS data at the time of the primary analysis, analyses of PFS and OS may be repeated when data are mature.

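### The pooled 80%-deaths rule has no minimum follow-up, so late-enrolled survivors in Cohorts 2 and 3 can be censored before the 56-week OS endpoint

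*Protocol*

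**What the plan says.** Section 2 of the protocol lists as a secondary endpoint of dose expansion "OS at 24 and 56 weeks and overall for each cohort", with PFS at the same times.

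Several places govern how long survival is followed:

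- Protocol 9.4, repeated in Table 11 footnote y: "Survival follow-up will continue for 2 years for each subject or until 80% of subjects enrolled have died".
- Protocol 3.5.2, repeated in SAP 3.1: "The study may end prior to this if 80% of enrolled subjects are deceased prior to the collection of the last survival follow-up".
- SAP 3.1, in the next paragraph: "Survival follow-up will continue for 2 years for each subject or until 80% of treated subjects have died". The denominator has changed from enrolled to treated.
- Protocol 3.5.1 and SAP 3.1: survival follow-up after stopping drug runs for 2 years from first dose, with no 80% exception.

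None of these counts deaths by cohort or sets a minimum follow-up. The bare *or* in 9.4 does not say whether the first or the later of the two limits governs.

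Primary completion is expected about 6 months after the last enrolment (3.5.2). For later data, SAP 4.3 says only that "analyses of PFS and OS may be repeated when data are mature". Cohorts 1 and 4 are closed; Cohorts 2 and 3 are not.

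**The concern.** The endpoint is defined per cohort, but the rule that can end its data collection is pooled. About 48 of the planned subjects come from escalation and are outside the PFS and OS objective, yet their deaths count toward the trigger. The first subject entered in 4Q2015, so much of the count can be supplied by early entrants. Those whose follow-up is cut are the survivors who entered last, and these are in Cohorts 2 and 3.

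Nothing else secures the 56-week estimate. The expected primary completion falls short of 56 weeks for the last entrants, and the repeat analysis is optional and of little use if collection has stopped. Survivors are censored at last contact (SAP 15.3) and contacts are 16-weekly, so some follow-up before the stop date may be lost as well.

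Active AESI collection also runs through survival follow-up (9.4, footnote y) and would end at the same time.

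**Working it through.** **The plan's own figures.** The 80% cut-off has no stated derivation. The one calculated design figure, at least 3 responders of 20, reproduces by exact binomial: P(X≥3 | 5%) = 0.0755 (stated 8%) and P(X≤2 | 20%) = 0.2061 (stated 21%). It does not bear on this point.

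**Step 1: the trigger.** Section 4.1: "A total of approximately 120 subjects will be enrolled in this study", that is 48 + 72. On Cohort 4, Section 14.2.1 says: "Sufficient information to describe the PK of tazemetostat was obtained after administration of tazemetostat tablets to 4 pediatric subjects". If the other groups fill, the total is 48 + 20 + 20 + 20 + 4 = 112.

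- 0.80 × 120 = 96 deaths, leaving 24 alive.
- 0.80 × 112 = 89.6, so 90 deaths, leaving 22 alive.

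**Step 2: when it can be reached.** Survival is followed for 2 years per subject, so 80% dead requires pooled 2-year OS of 20% or less. With exponential survival the median must be at most 24 × ln 2 / ln 5 = 10.3 months. Withdrawals and losses make the trigger harder to reach.

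**Step 3: which time point is exposed.** Six months is about 26 weeks. At primary completion every living subject still followed has passed 24 weeks, but those enrolled in the last 56 − 26 = 30 weeks of accrual have not reached 56.

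**Step 4: size, by simulation.** The following assumptions are not in the documents:

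- exponential survival;
- escalation entry over weeks 0–85 and Cohorts 1 and 4 over weeks 85–180;
- Cohorts 2 and 3 entering from week 85 or 130 to week 235;
- Cohort 3 median OS of 9 to 24 months, never below the others';
- N = 112, and no stop before enrolment ends.

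The 16-weekly contact interval is not modelled. Each table cell gives the chance that at least one living Cohort 3 subject is cut before 56 weeks, then the mean number cut out of 20.

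| Median OS of all others | Stop allowed once enrolment ends | Stop allowed from 26 weeks after last enrolment |
|---|---|---|
| 3–6 months | 0.92–1.00; about 5–9 | 0.91–0.99; 2.2–4.7 |
| 9 months | 0.13–0.73; 0.4–2.3 | 0.17–0.69; 0.4–1.7 |
| 12 months | 0.04 or less; 0.1 or less | 0.05 or less; about 0.1 or less |

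For 24 weeks, a stop as soon as enrolment ends gives chances of 0.56–1.00, 0.02–0.43 and 0.01 or less in the three rows. If follow-up runs to primary completion, the chance is zero in every setting.

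**Step 5: effect on the estimate.** Take a median of 6 months for the others, 12 months for Cohort 3, and entry to Cohorts 2 and 3 from week 130. With full follow-up, 20 × 2^(−12.9/12) = 9.5 subjects are at risk at 56 weeks (56 weeks = 12.9 months). This falls to about 6.7 if the stop waits for primary completion, and to about 5.2 if it may come when enrolment ends. The mean 95% CI half-width for 56-week OS goes from 0.21 to 0.23 and 0.25.

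**The case against.** **Early ending is optional and may not be planned.** Section 3.5.2 is permissive, 9.4 does not say which limit comes first, and the synopsis projects the last visit for 2Q2022, more than 2 years after the Amendment 8 date of 20 February 2020 given in SAP 1. This stands. It means the cut is allowed, not intended.

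**The trigger may never be reached.** This also stands. Above a pooled median of about 10 months little or nothing is cut. The documents give no OS by cohort. The 28% of pediatric subjects who died on treatment or within 30 days (1.4.2) makes high mortality plausible but does not settle 2-year OS.

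**The harm is limited.** Kaplan-Meier handles administrative censoring, and these are descriptive estimates in about 20 subjects. This stands in the main. Section 5.3 links later entry to a changed starting dose for some subjects, so strictly non-informative censoring is not guaranteed, but nothing in the documents shows a bias.

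A reader might infer more than the documents support:

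- *Cohort 3 is the victim because its subjects live longer.* The only hint is response and stable-disease data in 8 pediatric epithelioid sarcoma subjects (Table 1). Section 1.2 describes renal medullary carcinoma and myoepithelial carcinoma, both Cohort 3 tumors, as rapidly fatal or of short survival. Cohort 2 is still open too and is equally exposed. Nor does the result need longer survival: with every median at 9 months and a stop allowed from primary completion, the chance is still 0.67–0.69.
- *The rule can fire with all 20 Cohort 3 subjects alive.* This is arithmetically possible, but it needs 96 of 100 or 90 of 92 of all others dead (96% or 98%).
- *Almost half of subjects lack 56 weeks at the primary analysis.* That is 30/65 = 46%, from the nominal 15-month accrual. The trial's dates contradict it: from the expansion decision on 06-Jul-2017 to 20 February 2020 is about 137 weeks, and 30/137 = 22% under uniform accrual, less if enrolment closed later. The figure also describes the primary-analysis cut, not the 80% rule.
- *PFS is cut in the same way.* Disease assessments after treatment run to progression or death without an 80% cap (9.4, footnote x). PFS is exposed only through the optional study end in 3.5.2.
- *All late AESI reporting stops.* Section 10.9 keeps secondary lymphoma reportable beyond 30 days after the last dose. Sections 10.4.1 and 10.4.2 were not available to me and may add further duties.

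**Conclusion.** The gap is real but conditional. The plan lets one pooled death count end data collection for a per-cohort 56-week endpoint, with no minimum follow-up, two denominators and an unstated order between 2 years and 80%.

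If pooled 2-year OS is about 20% or less, late-entering survivors in Cohorts 2 and 3 can be censored before 56 weeks. Under the assumptions above, with follow-up to primary completion and a median of 3–6 months in the other subjects, between 2 and 5 of 20 Cohort 3 subjects are lost on average. At 9 months it is fewer than 2, and at 12 months almost none. The cost is fewer subjects at risk, a somewhat wider interval, and an earlier end to active AESI collection for those children. The 24-week estimate is safe if follow-up reaches the expected primary completion.

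The documents do not support saying that the trial cannot meet its survival objective. The point is worth fixing because the remedy is cheap.

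**What to change.** In protocol 3.5.2, 9.4 and Table 11 footnote y, and in SAP 3.1:

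1. Use one denominator, treated subjects.
2. State whether the 2-year limit or the 80% limit governs, and reconcile this with 3.5.1.
3. Add: *The 80% provision may not be applied until every living expansion subject has at least 56 weeks from first dose, or has withdrawn or been lost to follow-up.*

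In SAP 4.3, replace the optional repeat with: *PFS and OS will be analyzed again once all expansion subjects have 56 weeks of follow-up, have died or are lost.*

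By construction no expansion subject can then be cut by the 80% rule before 24 or 56 weeks. Applying the 80% count within each cohort instead would be worse: it leaves about 48 escalation subjects without a rule, and in Cohort 4 (n = 4) it would require all four deaths.

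The cost is a few more 16-weekly remote contacts for the few recent survivors, already foreseen under the 2-year follow-up, and a somewhat later earliest possible study end.
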